**TABLE 1. TIMELINE OF STUDY EVALUATION AND MEASUREMENT COMPLETION**

| Measures: BOTH OST-S and TAU Conditions  | Respondent:                          | Screening/Eligibility | Pre-treatment/ Baseline |  | Post-treatment               | 5M Follow-up | 12M Follow-up |
|--|--------------------------------------|-----------------------|-------------------------|--|------------------------------|--------------|---------------|
| Measures of Proximal Student Outcomes   |                                      |                       |                         |  |                              |              |               |
| Children's Organizational Skills Scale (COSS)—Teacher (COSS-T)   | Teacher                              |                       | X                       |  | X                            | X            | X             |
| Children's Organizational Skills Scale (COSS)—Parent (COSS-P)  | Parent                               |                       | X                       |  | X                            | X            | X             |
| Patterns of Adaptive Learning Scales (PALS) – Academic Efficiency Subscale                                     | Student                              |                       | X                       |  | X                            | X            | X             |
| Measures of Distal Student Outcomes   |                                      |                       |                         |  |                              |              |               |
| Academic Progress Report (APR)   | Teacher                              |                       | X                       |  | X                            | X            | X             |
| Academic Competence Evaluation Scales (ACES) - Reading/ Language Arts & Mathematics Subscales ONLY             | Teacher                              |                       | X                       |  | X                            | X            | X             |
| Academic Grades  | Study team                           |                       | X                       |  | X                            | X            | X             |
| Student Homework Completion Survey   | Teacher                              |                       | X                       |  | X                            | X            | X             |

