### 2.1 Primary Objectives (or Aims)

The primary objectives of this study are:

- Determine the efficacy of OST-S with regard to improving **proximal student outcomes** (OTMP skills, academic self-efficacy) relative to a treatment as usual control group (TAU) at post-treatment, as well as 5-month and 12-month follow-up.
- Determine the efficacy of OST-S with regard to improving **distal student outcomes** (academic productivity and grades) relative to TAU at post-treatment, as well as 5-month and 12-month follow up.

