## 5.2 Measures of Proximal Outcomes and Mediators – OTMP Skills and Student Academic Self-efficacy

Measures will be completed at baseline, post-treatment, and at 5-month and 12-month follow-up.

**Children's Organizational Skills Scale, Parent (COSS-P) and Teacher (COSS-T) Versions.** The COSS-P and COSS-T ([name] & [name], 2009) will be used to assess OTMP functioning at home and school. COSS total scores have good discriminant validity and are sensitive to treatment effects ([name] et al., 2013; Pfiffner et al., 2013). Each COSS version uses a 4-point rating scale (1=*Hardly ever or never* to 4=*Just about all of the time*). Although the COSS yields three subscale scores, only the total score will be used to reduce the number of measures in the analyses.

**Patterns of Adaptive Learning Scales – Academic Efficacy Subscale (PALS).** The 5-item Academic Efficacy subscale of the PALS (Midgley et al., 1998) will be used to evaluate students' perceptions of their competence in completing their classwork. Items are rated on a 5-item scale from 1 = not at all true to 5 = very true.

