## **6 STATISTICAL CONSIDERATIONS**

### **6.1 Main Study Analysis**

#### **6.1.1 Study Aims**

**Aims 1 and 2: Effect of Intervention on Proximal and Distal Outcomes.** Linear mixed effects models with random intercepts and slopes for school (the cluster), and fixed effects for intervention, time, and time-by-intervention interaction (the estimate of interest) will be applied. Random effects account for inter-school variation in the effect of the intervention over time.

**Aim 3: Mediation Effects.** This aim explores the effect of potential mediating variables (M; OTMP skills, self-efficacy) on the effect of the intervention (A) on student academic outcome (Y). Our goal is to understand the mechanism of change in student performance due to the planned intervention. In this context, we will examine two levels of mediation: school-level average organization skills associated with school-level academic performance, and student-level organization skills and performance.

**Aim 4: Association Between Fidelity/Engagement and Outcomes:** To determine whether fidelity and engagement are associated with outcomes, we will describe the impact of these factors on outcomes, with special attention to variation in outcomes across schools. These associations will not benefit from randomization (fidelity and engagement are post randomization interim process endpoints). For that reason, our assessments will be largely descriptive and qualitative, and will include assessment during the follow-up periods.

**Aim 5: Effect Modification:** Aim 5 explores potential moderating variables (i.e., gender, grade level, family SES, special education status, and severity of ADHD, externalizing and internalizing behaviors). Because these potential effect modifiers vary within the unit of randomization (school), these contrasts are essential within-cluster comparisons with good statistical power (see below). Effect modification can be estimated using the mixed effects and longitudinal models outlined previously.

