### 6.1.2 Primary Endpoint

The primary endpoints are student OTMP skills and student academic self-efficacy, measured at post-treatment, 5 months from baseline and 12 months from baseline and compared between the intervention condition and the TAU condition.

---

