Linear mixed effects models were used to estimate the effects of OST-T2 on outcomes. Models had three levels: assessment time nested within student and students nested within school. All models included time (as splines), treatment, and time-by-treatment interactions. Mixed effects models included random intercepts for school (to account for clustering of students within schools), random slopes (over time) to allow for different trajectories across schools, and a random intercept and random slope for student to allow for variation in the effect of treatment assignment across students over time. Modeling for the clustering effect of schools accounted for more than one student being rated by multiple teachers; teachers rated a mean of 1.6 students and approximately 85% of teachers rated three or fewer students at each time point. Statistical significance was evaluated using a threshold p value of .0083, accounting for the estimation of three contrasts of time-by-treatment differences per outcome and two measures per domain (OTMP skills [COSS-P, COSS-T], homework performance [HPC, HPQ-T], and academic performance [ACES, APS]).

Mixed effects models facilitated both the graphic display, and contrasts, of curves depicting the expected values of outcomes over time from time zero until 12-month follow-up for the student with the last data collected. All confidence bounds reflected variances based on the multi-level linear model. To evaluate differences between conditions, we estimated model-based, expected values for outcomes at four preplanned times, 0 (baseline), 14 (post-treatment), 22 (5-month follow-up) and 55 (12-month follow-up) weeks, except for academic grades, which

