were estimated for beginning and end of school year. Those actual times were translated into their equivalent values in the models for restricted cubic splines. Expected values were then the product of these times and estimated coefficients from the mixed effects models. The primary overall estimate of intervention effect for each outcome was the between-group difference of the change in expected values (means) from time zero to the prespecified outcome assessment times. The mixed effects models applied in this study assume that missing scores were missing at random, a reasonable assumption given that we also adjusted for student baseline covariates that might explain missed assessments. Analyses used all available scores, consistent with an ITT approach. Sensitivity analyses were conducted to determine whether data collected after the school shutdown due to the COVID-19 pandemic (March 16, 2020) altered study findings.

Mixed effects models were also used to estimate student-level outcomes at each assessment time. We estimated random effects for students and schools to determine model-based estimates, which reflect expected values (average score of the entire group) plus individual random effects (departures of the individuals from average). Statistical theory suggests that model-based predictions provide better estimates of true values than the actual data. Model-based predictions, called “empirical Bayes” estimates, combine individual measures with group-level expected values in a manner that permits individual estimates to derive strength from the group effects (Efron & Morris, 1973). Using these estimates for each student at each assessment point, we categorized all students based on thresholds derived from normative data sets or common-sense scale values on measures. For the COSS-P, COSS-T, HPC, and HPQ-T, thresholds were set at one-half standard deviation below/above the mean of the normative sample to indicate performance within the normal range (for normative information, see masked for review; [name] et al., 2006; [name] et al., 2007), as this corresponds with a medium effect size. For the ACES and APS, threshold values were set at a value reflecting performance at the standard for grade level (3.0) or above. For academic grades, the threshold was set at a value of 3.0 or above.

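### The SAP never names academic self-efficacy (PALS), a protocol primary endpoint, and does not say which significance threshold applies to it

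*SAP*

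**What the plan says.** Protocol 6.1.2 is explicit: "The primary endpoints are student OTMP skills and student academic self-efficacy", compared between arms at post-treatment, 5 months and 12 months. The first primary objective in 2.1 names the same pair ("OTMP skills, academic self-efficacy) relative to a treatment as usual control group (TAU) at post-treatment, as well as 5-month and 12-month follow-up"). Section 5.2 assigns the five-item, student-rated PALS subscale to self-efficacy and says of the proximal measures: "Measures will be completed at baseline, post-treatment, and at 5-month and 12-month follow-up". Table 1 schedules it at all four times, as "Patterns of Adaptive Learning Scales (PALS) – Academic Efficiency Subscale" (5.2 calls the subscale Academic Efficacy). Section 6.1.3 does not list self-efficacy among the secondary endpoints.

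For proximal and distal outcomes in general, protocol 6.1.1 plans a linear mixed model in which "fixed effects for intervention, time, and time-by-intervention interaction (the estimate of interest) will be applied".

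The SAP names COSS-P, COSS-T, HPC, HPQ-T, ACES, APS and academic grades. On error control it says "Statistical significance was evaluated using a threshold p value of .0083", derived from three contrasts per outcome and "two measures per domain (OTMP skills [COSS-P, COSS-T], homework performance [HPC, HPQ-T], and academic performance [ACES, APS"). On estimation it says "The primary overall estimate of intervention effect for each outcome was the between-group difference of the change in expected values", taken from time zero to each assessment time. Its thresholds for classifying individual students cover the seven named outcomes only.

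**The concern.** An SAP should let a reader trace every primary endpoint to a model, a contrast and a decision rule. For self-efficacy that trace breaks at the SAP. Someone working from the SAP's list of measures would produce no PALS result and would still appear to have followed the plan, while protocol 6.1.2 went unfulfilled. Someone who did analyse PALS would have to decide afterwards which threshold applied. Both routes leave room for selective reporting of a primary endpoint.

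There is a downstream effect. Aim 6 in protocol 6.1.1 builds an incremental cost-effectiveness ratio only for outcomes that differ significantly from control, and 2.2 lists self-efficacy among the outcomes for the cost objective. Whether self-efficacy qualifies depends on a criterion that is not explicitly assigned to it.

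**Working it through.** **1. Coverage.** Table 1 lists nine proximal and distal outcome measures: COSS-T, COSS-P, PALS, APR, ACES, grades, homework survey, HPQ-T and HPC. The SAP names seven, taking its APS to be the protocol's APR (an assumption). The two missing are PALS and the one-question homework survey. Under 6.1.2 the primary measures are COSS-P, COSS-T and PALS, so two of three are named and PALS is the only primary measure left out.

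**2. The SAP's own threshold.** Inputs from the SAP are 3 contrasts and 2 measures per domain. The base alpha is not stated; 0.05 is inferred because it reproduces the figure:
- 0.05 / (3 × 2) = 0.05/6 = 0.00833, which matches .0083.
- A Šidák version, 1 − 0.95^(1/6) = 0.00851, does not match.

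The correction is therefore Bonferroni within a domain. All six tests in each listed domain are used, and none of the three domains is self-efficacy.

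**3. What PALS would get.** The answer depends on a choice the SAP has not made:
- PALS as its own one-measure domain: 3 contrasts, 0.05/3 = 0.0167. The .0083 for the other domains is unchanged.
- COSS-P, COSS-T and PALS as one primary family: 3 × 3 = 9 contrasts, 0.05/9 = 0.0056. Keeping 0.05/6 for all nine would allow up to 9 × 0.00833 = 0.075, or 1 − (1 − 0.00833)^9 = 0.073 if the tests were independent.

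The two candidates differ by a factor of three (0.0167/0.0056).

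**4. Power cost of the joint family only.** Inputs are 0.5 SD, 120 students per arm (protocol 6.1.4), and a noncentral t with 20 − 2 = 18 df, with SE = SD of change × √(2 × design effect / 120). Power when moving from 0.00833 to 0.00556:

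| Within-student correlation | Protocol's printed values (design effect 1.11; change SD 0.6, 0.8, 1.0) | Recomputed values (design effect 1 + 11 × 0.038 = 1.418; change SD √(2(1 − corr))) |
|---|---|---|
| 0.7 | 0.998 to 0.996 | 0.874 to 0.834 |
| 0.6 | 0.933 to 0.906 | 0.740 to 0.682 |
| 0.5 | 0.751 to 0.694 | 0.618 to 0.553 |

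The loss is about 0.002 to 0.06 in the first column and 0.04 to 0.065 in the second. With PALS as its own domain there is no loss for the other measures.

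**5. Search for a recorded change of status.** Protocol 6.2.1 refers to OTMP skills as the primary study outcome, in the singular. It does so to limit a one-time preliminary analysis, and the same section says the goals of that analysis are not new aims. Protocol 6.2.2 foresees an amendment to clarify aims, but only if a funding supplement is obtained, and no resulting change of endpoints is in the supplied text. Section 6.1.2 still lists both endpoints.

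**The case against.** The strongest reply is that PALS is covered without being named. Protocol 6.1.1 commits to a mixed model for proximal outcomes, the SAP defines its effect for each outcome, and the .0083 sentence can be read as a general rule with the parenthesis only explaining its origin. Academic grades also lie outside the three counted domains and are still analysed. The SAP text is short and silent on Aims 3 to 6 as well, so the gap may come from its limited scope.

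Much of this stands. A reader might infer that the documents provide no threshold for self-efficacy at all; that goes too far, because .0083 may be meant to apply. The accurate statement is that its application to PALS is not explicit. Grades do not close the gap: the SAP names them and gives them their own assessment times and cut-off, whereas PALS gets nothing. Limited scope does not explain it either, since the text sets out the treatment-effect analysis to which self-efficacy belongs under Aim 1.

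A reader might also infer that the omission inflates type I error to 0.075. The SAP does not support that. Its control is within domain, and under that logic PALS as a separate construct would get 0.0167 and disturb nothing else. The 0.075, 0.0056 and power-loss figures hold only for a joint family that the SAP never adopts.

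Finally, a reader might infer that PALS was dropped after its results were seen. The observed data in the SAP concern medication rates, covariate balance, assessment timing and ratings per teacher. It prints no outcome result, and the data set for the preliminary analysis held only COSS-P and COSS-T as outcomes. The text does not show that PALS results were known.

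**Conclusion.** The point holds as a gap between protocol and SAP on a declared primary endpoint: self-efficacy is primary in 2.1 and 6.1.2, unnamed in the SAP, without a domain in the .0083 derivation, and nowhere recorded as demoted. It is more than missing detail, because following the SAP's list of measures leaves the endpoint untested or its reporting optional. The arithmetic of .0083 is correct and is not the fault. The size is one of three primary measures, with a candidate threshold between 0.0056 and 0.0167 depending on the family chosen.

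This rests on an inferred base alpha of 0.05, on APS being the APR, and on 6.1.2 defining what is primary. Section 2.1 also places academic productivity and grades under the primary objectives while 6.1.3 makes academic outcomes secondary, so the count of primary measures depends on which section governs.

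**What to change.** - Name PALS in the SAP, with the same mixed model and the three baseline-to-time contrasts, and report the result whatever it shows.
- State its family and threshold: 0.0167 as a one-measure domain, leaving .0083 elsewhere, or 0.0056 for COSS-P, COSS-T and PALS as one primary family.
- State that this choice was made after the SAP had been written with trial data in hand, and whether PALS results had been seen by then.
- If self-efficacy was demoted, give the date and reason, and still report it.
- Reconcile protocol 2.1 with 6.1.2 and 6.1.3 on which outcomes are primary.

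The cost is a few sentences and one more model on data already scheduled for collection. Only the joint-family option costs power, by the amounts shown in the working.

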## 5.3 Measures of Distal Outcomes – Academic Outcomes

Measures will be completed at pre- and post-treatment, and at 5-month and 12-month follow-up.

**Academic Progress Report** (APR; [name] et al., 2013). The APR is a teacher-report measure that assesses proficiency in seven academic subjects relative to standard expectations (1=*Well below standard* expected at this time of year; 3=*At standard*; 5=*Well above standard*). The sum of ratings across seven academic subjects is the unit of analysis. Reliability is acceptable ( $\alpha = .84$ ), and this measure is sensitive to OST treatment effects ([name] et al., 2013).

**Academic Competence Evaluation Scales** (ACES; DiPerna & Elliott, 2000). The ACES is a teacher-report scale that assesses the academic competence of students in kindergarten through grade 12. The Reading/Language Arts and Math subscales of this measure will be used. Alpha coefficients and test-retest correlations for these subscales have been shown to be above .90. The average of these subscale scores will be used in the analyses.

**Academic Grades.** We will obtain student report card grades for students in OST-S/TAU. We will calculate students' grade point average based on report card grades.

**Homework Survey:** Teachers will be asked to complete one question related to the percentage of homework assigned (in the school year to date) that they student has turned-in.

**Homework Performance Questionnaire – Teacher Version** (HPQ-T). The HPQ-T assesses students' homework behavior during the past 4 weeks. Each item is rated on a five-point scale. The 9-item Student Self-Regulation factor will be used in the analyses. This factor has been demonstrated to have strong psychometric properties ([name] et al., 2014).

**Homework Problem Checklist (HPC).** The HPC is a 20-item parent-report measure that assesses student homework performance. The psychometric properties of this instrument have been shown to be acceptable ([name] et al., 2006), and the HPC was sensitive to

treatment effects in the OST-C study ([name] et al., 2013). The total HPC score will be used in the analyses.

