### 6.1.3 Secondary Endpoints

The secondary endpoints are student academic productivity, homework, and academic grades.

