#### **8.7 Payment to Subjects/Families**

**Parent/Legal Guardian/Caregiver Stipends.** All parents/legal guardians/caregivers completing measures will be given a stipend of \$30 for completing assessment forms at each time point. Forms will be collected at four time points: baseline, post treatment, 5-month follow-up and 12-month follow-up.

**Student Compensation.** Student participants will receive small prizes (valued at \$2 or less) for actively participating in study sessions and for completion of measures at four time points: baseline, post-treatment, 5-month follow-up and 12-month follow-up.

**Teacher Stipends.** Teachers of participating students will be given a stipend of \$30 per student for completing assessment forms at each study assessment time point. Forms will be collected from all participants at baseline, post-treatment, 5-month follow-up, and 12-month follow up.

---

**School Staff Buyout Time.** For their work collaborating with us in conducting the OST-S groups, school partners' time will be bought out so that the school can pay for replacement staff during this time. Our budget calculations assume that for each OST-S group, a school partner will work with us 4 hours a week during the 8 weeks of the OST-S group, running two group sessions a week, preparing for the group, consulting with teachers and parents and meeting with study team trainers for consultation and coaching. In addition, we are assuming that each year they run groups, school staff will spend up to 8 hours in training during the weeks prior to running the first of the two groups. We have also allocated 4 hours per group for both OST-S and TAU groups to compensate the time that they spend assisting in the eligibility assessment and consent process (contacting families).

**School Partner Stipends.** In addition to school staff buy-out, school partners in both conditions will be compensated \$50 for their effort in assisting with student recruitment of two OST-S groups (up to 4 students each) (contacting families, collecting referral forms from teachers, and collaborating with CHOP staff). The stipend will be provided to the school partner each year after the eligible students are enrolled for that particular school year. If two school partners assist with the recruitment of students each school partner will receive \$25 for assistance in recruiting one OST-S group (up to 4 students).

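### Grades are estimated at the start and end of an unnamed school year, not at the post-treatment, 5-month and 12-month points that the protocol sets

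*SAP*

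**What the plan says.** Protocol section 2.1 lists grades among the distal outcomes and asks for the effect on "academic productivity and grades) relative to TAU at post-treatment, as well as 5-month and 12-month follow up". Section 5.3 gives the collection schedule for these outcomes: "Measures will be completed at pre- and post-treatment, and at 5-month and 12-month follow-up". It defines the measure as "grade point average based on report card grades". In Table 1 the row "Academic Grades" is marked at baseline and at all three follow-ups. Section 6.1.3 fixes the status: "The secondary endpoints are student academic productivity, homework, and academic grades".

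The SAP sets time zero at consent, models time as continuous, and estimates outcomes at weeks 0, 14, 22 and 55, "except for academic grades, which" "were estimated for beginning and end of school year". It does not say which school year is meant, why grades differ, or where those two points lie in weeks from consent. In the same paragraph it defines the effect for each outcome as the difference between arms in change from time zero.

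**The concern.** The protocol promises a grade comparison at three times after baseline, and the SAP plans it at none of them. Grades come from report cards rather than from questionnaires about the student's organisation, so they are a useful complement to the rating scales, and whether any effect persists to 12 months is part of the stated objective.

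The calendar anchors raise a second issue. Each school runs more than one group a year, so the start and end of the school year may lie at different distances from treatment for different students. A single start-to-end contrast would then average over unequal lengths of follow-up.

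**Working it through.** **1. Time points side by side.**
- Protocol 2.1, 5.3 and Table 1: baseline, post-treatment, 5 months, 12 months.
- SAP, other outcomes: weeks 0, 14, 22, 55 from consent.
- SAP, grades: start and end of a school year, year not given.

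No stated follow-up time appears in the grades plan.

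**2. Starting point.** Suppose consent and baseline fall s weeks into a school year of L weeks. Then, in study time:
- start of year = −s
- end of year = L − s

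The start of the year equals time zero only if s = 0. Otherwise it lies before consent and differs between students, so it is not the origin that the SAP uses for each outcome's effect.

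**3. Reach of a single school year.** The documents give no calendar. I assume L = 36 to 42 and s = 2 to 28.
- L = 40, s = 4: start −4, end +36, which is past week 22.
- L = 40, s = 24: start −24, end +16, between weeks 14 and 22.
- L = 40, s = 28: start −28, end +12, before week 14.
- Extremes for year-end: 36 − 28 = +8 and 42 − 2 = +40.

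The 12-month conclusion does not depend on these ranges. For consent within the school year, L − s cannot exceed L, and no school year lasts 55 weeks. Protocol section 3.3.2 itself places the 12-month follow-up in the next school year.

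**4. Two groups a year.** Section 3.3.2 plans 4 groups per school, and section 6.1.1 refers to both years of participation: 4 / 2 = 2 groups a year. Section 8.7 agrees, placing school staff "in training during the weeks prior to running the first of the two groups". If the groups run in sequence, s differs between them. In the L = 40 example, s = 4 against s = 24 separates year-end follow-up by 36 − 16 = 20 weeks. This is an illustration, not an estimate.

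**5. Significance threshold.** The SAP's .0083 reproduces as 0.05 / (3 contrasts × 2 measures) = 0.00833, taking an overall 0.05, which the SAP does not state. The three domains it lists are OTMP skills (COSS-P, COSS-T), homework (HPC, HPQ-T) and academic performance (ACES, APS). Grades are in none of them and appear to have one contrast, so they have no stated threshold.

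**6. What report cards can resolve.** Weeks 14 and 22 are 22 − 14 = 8 weeks apart. With four marking periods in a 36-week year (assumed), each lasts 36 / 4 = 9 weeks. Grades will often be unable to separate these two times, so a repair should not promise both.

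**The case against.** The best defence is practical: grades exist only at marking periods, and two follow-up points 8 weeks apart may fall within one. That is a plausible reason for the exception, and it limits what can be asked for. It does not explain the loss of the 12-month point, and the SAP does not offer it.

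The SAP also says that the estimation times were converted to their spline equivalents. This may mean that grade times are already mapped to study time, in which case part of the repair exists. The text is ambiguous. On a scale that starts at consent, the start of the school year has no single value; on a calendar scale, time zero is not consent. Nor is a single school year stated: if the SAP meant to run into the following year, a later point could be covered.

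Protocol section 3.1.4 allows measurement times to be changed, but case by case and with a documented reason. It does not cover a general change for one outcome.

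Three stronger inferences are tempting and not supported:
- A reader might conclude that the grades objective goes unanswered. It does not: a between-arm contrast of grade change remains, though not at the stated times.
- A reader might put a percentage on how far the effect is diluted, or say that the first grade of the year already contains session weeks. Both need group start weeks, marking-period dates and knowledge of whether the year-end grade is cumulative. None is given, and section 8.7 is budget text without dates.
- A reader might infer bias in favour of one arm. Nothing in the documents shows a direction.

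**Conclusion.** The concern holds as a mismatch between the protocol's grade time points and those in the SAP. Grades have no planned estimate at post-treatment, 5 months or 12 months, and the contrast does not start at time zero. If the enrolment year is meant, the 12-month contrast cannot be obtained. These conclusions rest on the text alone; only the last depends on which year was intended.

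Uneven distance from treatment across groups is possible, since two groups a year are planned, but its size is unknown. The year-end range of study weeks 8 to 40 rests on assumed calendars.

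Grades are a secondary endpoint, although they sit under a primary objective, and no sample size depends on this. The point should be fixed because it decides whether the trial can say anything about grades at 12 months.

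**What to change.** In the SAP:
- Give each marking-period grade its closing date, in weeks from consent, in both arms, and enter it in the existing continuous-time model.
- Take as baseline the last marking period closed at or before consent, or the previous year's final grade if none has closed.
- Report the between-arm change at one named post-treatment point within the enrolment year, stating that report cards may not separate weeks 14 and 22, and at the marking period nearest week 55.
- State the threshold for these two contrasts. With an overall 0.05 it would be 0.05 / 2 = 0.025 if grades form their own domain, or 0.05 / (6 + 2) = 0.00625 if they join the six academic-performance contrasts.
- Keep the start-to-end-of-year contrast as descriptive, name the school year, and declare it as a departure from the protocol schedule.

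The cost is SAP wording and date-coding of report cards that Table 1 already schedules. Some previous-year report cards may be needed for students who consent early in the year, and single marking-period grades are slightly less precise. No sample size changes.
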